Hospitalized patients with comorbid COPD who are at high risk for readmission will be recruited. Specifically patients with comorbid COPD who are to be discharged with (a) admission diagnosis of COPD (GOLD stage II or greater); AND (b) either a prior non-elective hospitalization (one in the past 12 months) OR active smoker. Such participants will undergo questionnaire-based screening for sleep-disordered breathing (STOP-BANG questionnaire) and if they have a high risk for SDB (≥ 3 points) will undergo an overnight portable sleep study for screening prior to hospital discharge (AHI ≥ 10 per hour; $>3\%$ oxygen desaturation for hypopneas). Sites may exercise the option of using the STOP-BANG questionnaire as a screening tool for the purposes of enriching the study population.

Participants who exhibit AHI ≥ 10 per hour; $>3\%$ oxygen desaturation for hypopneas based on the portable sleep test will undergo a PAP “wash in” daytime exposure for 30 minutes after adequate mask-fitting, on the therapy device (AVAPS- AE). Participants who fail to tolerate such therapy, or indicate that they would be unable to use such therapy at night, will not be randomized. Considering the “wash-in” is performed prior to randomization, such participants will not be included as part of the intention to treat (ITT) analysis.

After randomization and prior to discharge, participants will either be initiated on AVAPS-AE therapy (intervention arm) for 60 days or will be referred to the sleep center for further diagnostic testing and therapy initiation (standard of care arm). Participants will complete quality of life questionnaires (Functional outcomes of sleep questionnaire [FOSQ]) at baseline (in-person), and in 30 and 60 days (by mail) post discharge. If participants assigned to the intervention arm are discharged with home O₂ therapy, the O₂ will be entrained into the AVAPS-AE device for nighttime use. At time of hospital discharge, if participants in the intervention arm are not meeting conventional daytime and nighttime criteria for O₂ therapy [(SpO₂ $<88\%$ in room air –day) (> 5 continuous minutes SpO₂ $\leq 88\%$ - nighttime)], they will undergo AVAPS-AE therapy alone.

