Participants who are screened for enrollment will be entered on a screening log which will be maintained at the clinical site. Participants referred for screening will be given a thorough explanation of the study and the requirements for participation by the study coordinator or other qualified medical professional. If the participant is interested in the study, the investigator or a member of his/her staff should approach the patient to obtain written informed consent. The background of the proposed study, the benefits and risks of the procedures and study should be thoroughly explained to the participant. The participant must sign the consent form prior to enrollment. This form or a modification of it must have prior approval of the study site's Institutional Review Board (IRB). Failure to provide informed consent renders the participant ineligible for the study.

Up to 10 sites will be recruiting for this study. Up to 80 participants will be enrolled across all sites with the goal of 60 participants (N=60) completing the study (25% attrition rate). One site should not enroll more than 25% of total N.

VI. Study Procedures

Screening Assessment

Hospitalized patients with comorbid COPD who are at high risk for readmission will be recruited. Specifically patients with comorbid COPD who are about to be discharged, with (a) prior hospitalization (within the past 12 months) Such participants will undergo questionnaire-based screening for sleep-disordered breathing (STOP-BANG questionnaire) and if they have a high risk for SDB (≥ 3 points) will undergo an overnight screening portable sleep study the night prior to hospital discharge (AHI ≥ 10 per hour; $>3\%$ oxygen desaturation for hypopneas). Sites may exercise the option of using the STOP-BANG questionnaire as a screening tool for the purposes of enriching the study population.

Spirometry

Each participant will undergo a spirometric assessment, using a handheld Koko™ unit, to determine if they meet inclusion criteria.

Spirometry will be performed based on the "Standardization of Spirometry – 2005".¹¹ Acceptability and reproducibility criteria are summarized in Table 8 of the ATS document. Spirometry equipment must be calibrated with a 3L syringe prior to the first use daily. The results will be printed and maintained in a calibration log, which will routinely be monitored for compliance during monitoring visits. Spirometry

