Participants who exhibit AHI ≥ 10 per hour; $>3\%$ oxygen desaturation for hypopneas based on the portable sleep test will undergo exposure for 30 minutes after adequate mask-fitting on the therapy device (AVAPS- AE; see device settings under section below entitled, "Standard Procedures and measurements prior to discharge"). Participants who fail to tolerate such therapy, or indicate that they would be unable to use such therapy at night, will not be randomized. Considering the "wash-in" is performed prior to randomization, such participants will not be included as part of the intention to treat (ITT) analysis.

Participants that are placed on PAP therapy during admission and tolerate the therapy will not be subjected to this aspect of the trial. Their experience, during the hospital visit, with the therapy will count as the PAP Wash-In.

Standard Procedures and measurements prior to discharge

Room Air SpO₂ assessment/Supplemental Oxygen

A room air SpO₂ measurement will be used to make a determination if supplemental oxygen is required prior to hospital discharge. SpO₂ should be collected with the participant breathing room air for at least 15 minutes prior. If participants cannot maintain a SpO₂ of at least 90% on room air, supplemental oxygen will be prescribed. If the participant requires supplemental oxygen (according to the guidelines stated

A Pilot, Multi-Center, Randomized, Open-Label, Parallel Group Study to Assess the Effects of a Novel Application of Averaged Volume Assured Pressure Support Ventilation (AVAPS-AE) therapy on Re-hospitalization in Patients with Sleep-Disordered Breathing with co-morbid COPD.

Confidential

below), but was not previously prescribed supplemental oxygen, the study investigator will prescribe it for the participant.

Data collection will consist of key demographic characteristics including gender, age, height, and weight. In addition, a medical history, physical exam, vital signs, medication assessment and Charlson co-morbidity index will all be collected/obtained.

Quality of Life Questionnaires

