A Pilot, Multi-Center, Randomized, Open-Label, Parallel Group Study to Assess the Effects of a Novel Application of Averaged Volume Assured Pressure Support Ventilation (AVAPS-AE) therapy on Re-hospitalization in Patients with Sleep-Disordered Breathing with co-morbid COPD.

Confidential

Physical Exam	X		
Medication Assessment	X		
Bedside Spirometry	X		
Room Air SpO2 assesment	X		
Anthropometric measurements	X		
Stop -Bang Questionnaire	X		
20 minute PAP Wash-in	X		
QOL questionnaires (FOSQ and SF-36)	X	X	X
Charleston Co-Morbidity Index	X		
Overnight Portable Sleep Test	X		
Randomization	X		
Device Set up training/Mask fitting	X		
1 week PAP adherence assessment (Treatment Group only)		X	
Weekly phone calls to promote PAP and medication adherence		X	
30 day Healthcare utilization assessment and questionnaire Phone Call		X	
60 day Healthcare utilization assessment and questionnaire Phone call		X	
Transition Plan			X
Optional Registry			X

VII. Statistical Analysis

The method described by Cook and Lawless will be used to handle repeated hospitalizations, physician office visits, or emergency room visits in patients who may or may not also have a terminal event. All repeated hospitalizations that occur in patients will be counted. We will use the count-approach and the gap-time approach, described by Cook and Lawless because we are interested in studying event occurrence rates in the two groups as well as the time to occurrence of events. Analysis will be performed for both 30- and 60-days. Actuarial costs will be assessed in patients belonging to both the intervention and usual care arm. Unadjusted comparisons of these costs will be made by independent t-tests or non-parametric equivalent. Differences will be adjusted for potential confounders and other covariates in

A Pilot, Multi-Center, Randomized, Open-Label, Parallel Group Study to Assess the Effects of a Novel Application of Averaged Volume Assured Pressure Support Ventilation (AVAPS-AE) therapy on Re-hospitalization in Patients with Sleep-Disordered Breathing with co-morbid COPD.

Confidential

multivariate regression models, to include age, gender, race, body mass index, baseline severity of COPD, AVAPS-AE and medication adherence. Biologically plausible effect modification will be evaluated before significant confounders are selected by inspection of significance levels as well as impact of estimated coefficient for hypothesis variable.

Data and Safety Monitoring Plan:

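### The covariates for the adjusted cost comparison are to be chosen with the treatment coefficient in view and no final model is fixed; the Charlson index, already collected at baseline, is not among those named

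*Combined protocol and SAP*

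**What the plan says.** Section VII (Statistical Analysis) sets out the cost analysis in two steps: "Unadjusted comparisons of these costs will be made by independent t-tests or non-parametric equivalent. Differences will be adjusted for potential confounders and other covariates". The adjusted models are "multivariate regression models, to include age, gender, race, body mass index, baseline severity of COPD, AVAPS-AE and medication adherence". Effect modification is examined first, and then "significant confounders are selected by inspection of significance levels as well as impact of estimated coefficient for hypothesis variable". I read the hypothesis variable as treatment arm. No threshold, order of entry, final model or blinding of the selection is stated.

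The Charlson index is a baseline measurement. Section VI, under the procedures before discharge, says that "medication assessment and Charlson co-morbidity index will all be collected/obtained", and the Study Process Flow table lists it in the pre-discharge column (as "Charleston Co-Morbidity Index"). It does not appear in the covariate list.

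Prior admission is described in three ways. Section II recruits patients with "either a prior non-elective hospitalization (one in the past 12 months) OR active smoker". The Screening Assessment in Section VI describes patients "with (a) prior hospitalization (within the past 12 months"), without the smoking alternative. The numbered inclusion criteria in Section IV do not mention prior admission.

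**The concern.** Selecting confounders by how far they move the exposure coefficient is a habit from observational work. In a randomized trial, confounding is already dealt with in expectation, and covariates serve mainly to improve precision and to correct chance imbalance. Both aims are met by baseline variables named in advance. A choice made while looking at the treatment coefficient adds nothing to either aim, and the reported p-value and interval take no account of it. Open-label assignment makes this worse, because nothing in the plan keeps the analyst from seeing the arms while choosing.

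Two things are at stake: whether the error rate of the adjusted cost comparison can be stated in advance, and whether a small trial leaves unused a comorbidity measure that it already has.

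**Working it through.** **The plan's own figure.** Section V enrols up to 80 to obtain 60 completers at 25% attrition: 60 / (1 − 0.25) = 80, which reproduces. The documents give no alpha, power, effect size or SD, so those used below are assumptions.

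**Error rate of the selection step.** Null trials were simulated (no treatment effect) with equal arms, a continuous outcome such as log cost, and five baseline covariates standing for age, gender, race, body mass index and COPD severity. Assumptions: two-sided alpha 0.05; covariates jointly explaining R² = 0.1 or 0.3 of the variance; a 10% change in the treatment coefficient, or p < 0.05 for the covariate, as the mechanical cut-offs. With 4,000 trials per setting, the Monte Carlo SE at 5% is √(0.05 × 0.95 / 4,000) = 0.34 points.

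| N, R² | All five fixed | Change-in-estimate | Significance | Either rule | Best of 2⁵ = 32 sets |
|---|---|---|---|---|---|
| 60, 0.1 | 4.2% | 4.8% | 5.4% | 5.1% | 9.3% |
| 60, 0.3 | 4.7% | 4.3% | 6.2% | 5.2% | 13.2% |
| 80, 0.1 | 5.3% | 5.1% | 6.1% | 5.9% | 9.3% |
| 80, 0.3 | 5.2% | 4.4% | 5.8% | 5.5% | 14.1% |

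A separate set of 1,500 null trials per setting at N = 60 gave 10% to 16% for the best of 32 sets, which is where the top of the 9% to 16% range comes from. Mechanical rules therefore stay near nominal. The inflation comes from free choice among models.

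**Value of the Charlson index.** Adding one covariate with partial correlation r to the outcome multiplies the variance of the treatment estimate by about (1 − r²) × 58/57 at N = 60, the ratio being the cost of one degree of freedom.

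- r = 0.3: 0.91 × 58/57 = 0.926; equivalent N = 60 / 0.926 = 64.8, about 5 more.
- r = 0.4: 0.84 × 58/57 = 0.855; equivalent N = 60 / 0.855 = 70.2, about 10 more.

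The correlation must be partial, because age and COPD severity are already on the list. The documents give no value for it. For scale, at 30 per arm the chance difference in a baseline mean has SD √(2/30) = 0.26 of that variable's SD.

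**Room for covariates in an event model.** Section VII (Risks and Discomforts) expects 20.5% readmitted within 30 days: 0.205 × 60 = 12.3 participants, or 0.205 × 80 = 16.4. The seven listed covariates plus arm would have 12.3 / 8 = 1.5 readmitted participants per term. The primary composite also counts office, urgent care and emergency visits, so it should have more events than this.

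**The case against.** The strongest reply is that the rule as worded does not inflate type I error. The simulation supports this for any mechanical version. A reader might infer that selecting on the treatment coefficient is invalid in itself; the figures do not bear that out, and the plan does not prescribe picking the most favourable set. What stands is that the plan states no mechanical rule either. Selection by inspection, without a cut-off, is a matter of judgement, so the error rate cannot be given in advance.

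A reader might also infer that the primary endpoint is affected. By the order of the sentences, the adjustment follows the cost comparison, an unadjusted cost comparison is planned as well, and no covariates are stated for the recurrent-event or gap-time analyses. The documents do not support extending the point to the primary analysis.

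It is tempting to add that prior admission, a risk factor known for everyone, has been left out. That is not established. Under the Section II wording it can vary between participants. Under the Screening Assessment wording, some admission in the past 12 months is a condition for all, so an any-admission term could not be estimated and its omission would cost nothing. No section lists prior admission as a recorded data item. These passages must be reconciled first.

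Finally, the covariate list is open-ended, so the Charlson index is unnamed rather than barred. That is fair, but an open list is part of the problem: the index could be added or omitted after the results are seen. That this is a pilot with no stated alpha limits the consequence without removing it.

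**Conclusion.** The point holds for the adjusted cost comparison, a secondary endpoint. Its final model is not fixed, and the selection step lets covariates be chosen with the treatment effect in view. Mechanical use would leave type I error at about 4% to 6%; choosing the most favourable set would raise it to about 9% to 16%, under the assumed alpha, five covariates, R² of 0.1 to 0.3 and N of 60 to 80. The plan permits the second without prescribing it.

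The Charlson index is a baseline measure already being collected and not named. Its value, about 5 to 10 participants on 60, rests on an assumed partial correlation of 0.3 to 0.4. Nothing firm can be said about prior admission until the entry wording is settled. The adherence terms in the same list raise a different question, not judged here.

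**What to change.** Delete the selection sentence in Section VII (Statistical Analysis). Before database lock, fix a short list of baseline covariates for the cost model, for example GOLD stage (the randomization balancing factor), age and the Charlson index. Fit that one model whatever the p-values, and report effect modification as exploratory. The exact membership matters less than that the list is short, measured before randomization and settled in advance.

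Add prior non-elective admission only if Sections II, IV and VI are reconciled so that it varies between participants, and only if it is recorded for everyone.

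State whether the recurrent-event and time-to-event models are adjusted. If they are, fix those covariates in advance too and keep them few, given only about 12 participants expected to be readmitted by day 30.

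The cost is SAP wording; the Charlson index needs no new data. The downside is that the sponsor gives up choosing covariates after seeing results.

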- One week Device Adherence Assessment (Intervention Group)

During the first 2-7 business days post discharge, research staff will evaluate participant's device adherence via remote download. Participants with poor adherence to AVAPS-AE at home (adequate adherence defined as \geq 4 hours of use on at least 5 of the first 7 nights) will not be included in the "per-protocol analysis" (Such participants will, however, be considered in the intention to treat analysis). Per the investigators discretion, the device setting parameters may be adjusted at this time.

- Weekly Phone Follow-ups (Initial 30 days only):

Phone calls will be made weekly (\pm 2 business days) by the study coordinator to assess mask interface issues (Intervention group) and encourage adherence to AVAPS-AE (Intervention group) and medications (both intervention and SOC group). If participants require an additional visit related to issues noted above, this visit may occur either in the home or as an office to the study site.

- Day 30

At 30 days (\pm 2 business days) post discharge, participants in both Intervention and SOC groups will receive a phone call to determine if they had been admitted to this hospital, or had an unplanned visit to a physician's office or emergency room. Participants will be asked to complete FOSQ and SF-36 questionnaires. Participants will be given the option of completing the questionnaires verbally via phone call or completing handwritten copies and returned via direct mail. Postage paid return envelopes will be provided to participants who elect to complete and return the surveys by mail.

- Day 60

On day 60 (\pm 2 business days), participants in both Intervention and SOC groups will receive a phone call to determine if they had been admitted to this hospital, or had an unplanned visit to a physician's office or emergency room. Participants will be asked to complete a final FOSQ and SF-36 questionnaire. Participants will be given the option of completing the questionnaires verbally via phone call or completing handwritten copies and returned via direct mail. Postage paid return envelopes will be provided to participants who elect to complete and return the surveys by mail. Participants in both

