Each subject will be assigned an identifying number to maintain confidentiality. Records will be stored in a database format that can be read by a standard statistical package. The examination forms will be formatted to facilitate accurate data entry and editing, and programs will be written to allow range checks at entry with illegal values not accepted. Specific missing codes will identify non-obtainable data due to missed visits or skipped questions. The research coordinator will enter the data into the case report forms and the PI will proof read the forms. Data will be entered weekly and cross-checked with the original data forms at the end of the week. The data manager and the study coordinator will perform weekly data verification and protocol compliance checks. Case Report Forms will minimize data entry error.

Safety monitoring plan: Adverse event reporting will be monitored in accordance with the guidelines and regulations of the governing IRB. Any serious and/or unanticipated problems will be reported immediately to the Institutional Review Board (IRB) and Philips-Respironics, Inc. as required. The site-PI and coordinator will monitor adherence to the protocol and data quality standards, and monitor for patient safety and evidence for adverse or beneficial effects. The site-PI will prepare annual report for review by the IRB. The reports will include: screening and baseline data, efficacy data, safety and adverse data, subject enrollment data, and dropout data (number, reason, and at what study phase).

VII. Risks and Discomforts

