We believe that there are minimal risks to participating in this study. Adverse effects of Non-Invasive (NPPV) are usually minor and manageable. The masks may cause some discomfort and air pressure and flow have adverse effects. All adverse effects encountered, including mask discomfort, nasal or mouth congestion or dryness, eye irritation, gastric insufflation, and nasal bridge ulceration will be recorded on data sheets that are part of the case report form. NPPV has not been shown to cause sinusitis or bronchitis, but these will be recorded if they occur, as well. Other more serious adverse effects, such as pneumothorax or aspiration pneumonia, are distinctly unusual in the outpatient setting, but will be recorded if they occur. The risk of pneumothorax is rare, occurring in less than 1% of the participants. All adverse events will be reported to the IRB annually and at the time of study closure. All significant adverse events will be reported to the Institutional Review Board within 24 hours.

A Pilot, Multi-Center, Randomized, Open-Label, Parallel Group Study to Assess the Effects of a Novel Application of Averaged Volume Assured Pressure Support Ventilation (AVAPS-AE) therapy on Re-hospitalization in Patients with Sleep-Disordered Breathing with co-morbid COPD.

Confidential

Discomfort is unusual during the lung function testing (spirometry); however, some participants can experience shortness of breath, lightheadedness, fainting, increased blood pressure or heart rate, coughing, wheezing or chest tightness after performing the test. All testing will be conducted by a trained study staff

The study equipment that will be used by the participant has been tested to ensure safety. Should the AVAPS-AE device not perform as designed, ventilation could increase or decrease more than desired. This effect could be uncomfortable or awaken the participant. Additionally, there will be weekly-up phone calls to ensure there are no issues with the therapy. In the event there is an issue with either therapy, the participant can easily remove their interface device should it become uncomfortable or make breathing difficult.

An adverse event (AE) is any unfavorable and unintended sign, symptom, or disease temporally associated with the use of study medication, whether or not considered related to study medication.

AEs will include:

- Changes in the general condition of the patient
- Subjective symptoms offered by or elicited from the patient;

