- Signs observed by the investigator or study personnel;

All concurrent disease including any change in severity or frequency of pre-existing disease.

A serious AE is one that:

- Results in death
- Is an immediate threat to life
- Results in permanent disability

In addition, a serious AE is one that is judged by the investigator to be an important or medically significant event. Causality assessments of AEs: For all AEs, the investigator will provide an assessment of causal relationship to study device. Appropriate forms will be used for this purpose and filed in the case report forms and submitted to the IRB for review. They will be classified as related, possibly related, and not related. The severity will be adjudged as being mild, moderate, or severe. Due to the complicated medical conditions of the patient population being recruited into the study, SAEs including hospitalizations are to be expected. The expected 30 day Re-admission rate for the patient population enrolled in this study is 20.5 percent ^(4, 5).

Discomfort is unusual during the lung function testing (spirometry); however, participants can experience shortness of breath, lightheadedness, fainting, increased blood pressure or heart rate, coughing, wheezing or chest tightness after performing the test. All testing will be conducted by a trained study staff.

A Pilot, Multi-Center, Randomized, Open-Label, Parallel Group Study to Assess the Effects of a Novel Application of Averaged Volume Assured Pressure Support Ventilation (AVAPS-AE) therapy on Re-hospitalization in Patients with Sleep-Disordered Breathing with co-morbid COPD.

Confidential

Given the risks outlined, we believe that although there may be discomforts associated with the use of this device and study related procedures, the risks are minimal.

VIII. Potential Benefits

Although participation in this trial will not result in any direct benefit to the participant, they will be contributing to generalizable data that will help improve device design and function.

IX. Monitoring and Quality Assurance

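### The adverse event definition refers to a study medication that this device trial does not have, and the listed seriousness criteria omit hospitalization (minor safety-definition point)

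*Combined protocol and SAP*

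**What the plan says.** The relevant text is in the Risks and Discomforts section (numbered VII, as is Statistical Analysis).

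- **AE definition.** The wording used for an AE: "any unfavorable and unintended sign, symptom, or disease temporally associated with the use of study medication, whether or not considered related to study medication". The list of what AEs include is not limited to device users; its last item is "All concurrent disease including any change in severity or frequency of pre-existing disease".
- **Causality.** For every AE, "the investigator will provide an assessment of causal relationship to study device".
- **Seriousness.** Three bullets name death, immediate danger to life and lasting disability. The next paragraph opens with a catch-all: "In addition, a serious AE is one that is judged by the investigator to be an important or medically significant event". Later in that paragraph comes "Due to the complicated medical conditions of the patient population being recruited into the study, SAEs including hospitalizations are to be expected", followed by the expected 30-day readmission rate of 20.5%.
- **Reporting.** In the same section, "All significant adverse events will be reported to the Institutional Review Board within 24 hours". The Data and Safety Monitoring Plan uses different words: problems that are serious and/or unanticipated go to the IRB and the sponsor at once, as required.
- **Contacts.** Under Study Procedures, the weekly calls in the first 30 days cover mask problems and device adherence in the intervention arm and medication adherence in both arms. The day 30 and day 60 calls ask both arms about admissions and unplanned visits.

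**The concern.** Two working definitions do not fit the trial.

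First, the AE definition rests on an exposure that neither arm receives. The causality rule suggests that the device is meant. On that reading the definition fits SOC participants poorly: they are not given AVAPS-AE at discharge, and their only planned exposure is the short daytime wash-in, which patients already tolerating PAP in hospital skip.

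Second, readmission is the serious event this protocol most plainly expects, yet it is not a listed criterion. A site working from the bullets and its own judgement might not class an uncomplicated readmission as serious; a site that follows the later sentence would. The trial is open label, so that judgement is made with the arm known.

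At stake are the SAE class of readmissions, their expedited reporting, the consistency of what reaches the IRB and the monitoring committee, and the comparability between arms of AEs that lead to no care.

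**Working it through.** **1. Is either definition corrected elsewhere?** The AE definition says medication; the causality rule says device; the Study Procedures section sends home a device, to the intervention arm only. No other section restates the definition or adds a hospitalization criterion. Both problems stand in the current text.

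**2. How open is the class of a readmission?**

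| Text in Risks and Discomforts | Uncomplicated readmission |
|---|---|
| Three bullets | Not serious |
| Investigator catch-all | Serious if the investigator so judges |
| Later sentence on expected SAEs | Treated as serious |

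The three are compatible if hospitalizations are always SAEs, and that is the natural reading. They diverge only where a site stops at the criteria and does not regard the admission as medically significant.

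**3. Scale.** The inputs are 20.5% readmitted by 30 days (Risks and Discomforts); up to 80 enrolled for 60 completing at 25% attrition, up to 10 sites, and no site above 25% of the total (Study Enrollment); and reviews at 25%, 50% and 75% of target enrolment (Study Design).

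The stated enrolment reproduces: 60 / (1 − 0.25) = 80.

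Expected readmissions by day 30 = n × 0.205:

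| Group | n | Expected |
|---|---|---|
| All enrolled | 80 | 16.4 |
| Completers | 60 | 12.3 |
| Reviews at 25%, 50%, 75% of 80 | 20, 40, 60 | 4.1, 8.2, 12.3 |
| Average site (80 / 10) | 8 | 1.6 |
| Largest site (0.25 × 80) | 20 | 4.1 |
| Largest site if the total is 60 (0.25 × 60) | 15 | 3.1 |

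The review rows assume that everyone enrolled by then has 30 days of follow-up.

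**4. These are expectations, not limits.** Treating readmissions as binomial at 20.5%, the central 95% range for 80 patients is 10 to 24. For a 20-patient site it is 1 to 8, with about a 39% chance of more than 4. The counts also stop at day 30, while the study period runs to day 60.

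**5. What cannot be sized.** The documents do not give the share of readmissions that would be serious on any reading, so the number whose class is truly open is some unknown part of about 16, possibly close to none. They give no rate for AEs outside hospital, so any gap in SOC recording cannot be sized either.

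**6. What SOC participants are asked.** The calls as described include no open AE question for this arm. Study Design and Study Procedures do, however, collect admissions, diagnostic tests, medication changes and procedures from all participants, with discharge summaries and records of office and emergency visits. What remains is mainly symptoms for which no care was sought.

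**The case against.** The strongest reply is that intent is clear. The bullets are not exhaustive, the catch-all can take in any admission, and the later sentence calls hospitalizations SAEs. The medication wording looks like template carry-over, and the AE list is broad enough to suggest that both arms are meant. Differing words for what must be reported matter little, because the Data and Safety Monitoring Plan defers to the governing IRB's rules, and medically significant appears in the SAE definition as an anchor. Call scripts and case report forms are not in the documents, so an open AE question may exist there.

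Most of this stands, and it is why the point is minor. It does not remove the point: a descriptive sentence about expected events is weaker than a listed criterion, and the medication phrase is still the operative definition.

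A reader might infer more than the documents support:

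- *That hospitalizations are excluded from SAEs.* They are not; the rule is ambiguous.
- *That readmissions could be lost or the primary endpoint biased.* Study Design has all death and hospitalization reports collected and adjudicated, whatever their SAE label, and the committee monitors safety on a continuing basis.
- *That SOC events go unrecorded, or that the arms will be classified differently.* Knowledge of the arm makes a difference possible, but nothing in the documents shows one or gives its direction.

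**Conclusion.** The point holds as a minor safety-definition issue, not an analysis choice. The AE definition names an exposure the trial does not have, and the seriousness criteria leave out the event that the following text treats as an SAE. As a result, SAE classification and expedited reporting of readmissions may differ between sites, and the basis for recording AEs in the SOC arm is unclear. The primary endpoint is not affected.

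The scale rests on the protocol's own 20.5% rate applying to those enrolled, and on full enrolment of 80. The expected 16 or so is the pool of readmissions, not the number that would be misclassified.

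**What to change.** 1. Define an AE as any untoward sign, symptom or disease in any participant in either arm, from consent to day 60, and delete the reference to study medication. Starting at consent matters: spirometry and the sleep study come before the wash-in, and the protocol names fainting and chest tightness among the risks of spirometry.
2. Add *requires inpatient hospitalization or prolongs it* to the seriousness list for both arms. State that the index admission counts only if prolonged, and state any exemption of expected COPD readmissions from expedited reporting.
3. In Risks and Discomforts, replace significant with serious in the 24-hour rule. This is a minor alignment of wording.
4. Ask both arms the same open AE question at the existing weekly, day 30 and day 60 calls.

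The cost is protocol wording, one scripted question on calls both arms already receive, an AE page for SOC participants, some additional SAE forms and brief site retraining. No new visits are needed. If sites already class every readmission as serious, item 2 adds no forms for readmissions.
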